### 1.2.3 Dosing Duration Rationale

Dose-proportionality can be assessed at any point of observation following initiation of dosing. Intra-individual variability, however, can best be assessed at two sampling times not anticipated to vary based on PK principles. Essentially, by definition, this condition is achieved when steady-state has been reached. This study requires direct observation of dosing to rule out adherence as a cause for variation in drug concentrations. Therefore, we plan to begin sampling for intra-individual variability assessments as early as possible after dosing, balancing logistical difficulties (up to daily dosing for study staff and research participants) and PK limitations. Intracellular TFV-DP concentrations are estimated to achieve between 93% and 97% of steady-state Cmin (trough) concentrations after 4 half-lives and 5 half-lives, respectively, have elapsed after initiation of Truvada® dosing. Based on an estimated 150-hour TFV-DP intracellular half-life (FTC-TP will achieve steady-state earlier, given its far shorter 36-hour half-life), the 4 and 5 half-life points coincide with 28 and 35 days of dosing. Laboratory assay variation for all of the assays planned for this study are more than twice as large as the very small 4% difference in concentrations that we expect to measure between Day 28 and Day 35. Accordingly, we plan to dose for 35 days, and to use samples from Day 28 and Day 35 for our intra-individual variability estimates. One could argue for longer periods of dosing to further reduce differences between doses in the asymptomatic approach to a true steady-state, but we believe that our proposed plan provides a reasonable balance between logistical complexity (daily dosing under direct observation) and reasonable experimental variation.

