### **2.3.2 Study Sampling**

Sampling will occur over 7 weeks: at enrollment (pre-dose), pre-dose #2 (Day 1 for treatment arm 4, Day 3 for treatment arms 2 and 3, and Day 7 for treatment arm 1) and Days 7, 14, 21, 28, 35 and 49 to support each of the several objectives as follows:

1. Sample blood serum and blood cells (total cells and CD4+ cells) weekly for 5 weeks (Enrollment and Days 7, 14, 21, 28, and 35) to assess rate of accumulation and dose-proportionality in concentrations of extracellular TFV and FTC and intracellular TFV-DP and FTC-TP.
2. Sample blood serum and blood cells at steady-state (Day 28 and Day 35) to assess intra-individual variability.
3. When participants consent to participate in HPTN 066, they will be offered the opportunity to participate in the intensive sampling cohort (to provide mucosal samples). The slots in the intensive sampling cohort will be balanced by gender, so that there will be two men and two women who will undergo mucosal sampling in each of the four arms of the study. Potential research participants who do not choose to participate in or are ineligible for the intensive sampling cohort will be offered participation in the non-intensive cohort. The study team will sample rectosigmoid, seminal and vaginal fluid, cells, and tissue (in addition to blood) at Days 35 and 49 to compare extracellular concentrations of TFV and FTC and intracellular concentrations of TFV-DP and FTC-TP, and to estimate the elimination rate of drug from these compartments.

The sampling described must occur on the days prescribed given the need to synchronize post-dose time (7 days) across the four regimens. The blood sampling time should precede the established dosing time by no more than one hour. If the participant cannot have tissue sampled as prescribed, sampling should take place within the visit window, described in the SSP. In all cases, there must be accurate recording of sample collection times.

Biopsies will not be performed during menstruation. As such, the timing of the first dose will need to take into consideration menstrual patterns and will be adjusted accordingly.

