### **7.2 Endpoints**

#### **7.2.1 Primary Endpoints**

Consistent with the primary study objective, the following endpoint will be assessed on Day 28 and Day 35 across all 4 dosing arms:

- Concentrations of TFV and FTC in blood serum
- Concentrations of TFV-DP and FTC-TP in PBMCs and CD4+ blood cells

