## 7.3 Accrual, Follow-up, Retention, and Sample Size

A total of 32 evaluable men and women will be enrolled over a period of approximately 6 months at multiple sites. An equal number of participants (8 per arm) will be randomized into each of the four dosing arms. Each enrolled participant will be followed for 7 weeks.

Research participants may miss one of the following pre-steady-state study visits when on drug (Day 7, Day 14, Day 21) and remain in the study and remain eligible for evaluation in the PK outcome analysis of the study. Day 0, Day 28, Day 35, and Day 49 are required for a participant to be considered evaluable. Optimally, all study product dosing will occur on the date prescribed. However, some forgiveness of strict adherence to the schedule will be tolerated as long as the total dose within each week is consistent with the prescribed total. Therefore, for arms 1, 2, and 3, study drug dosing can be delayed by 2 days, during the first 3 weeks of the study. Thereafter, all doses in week 4 and 5 must be taken as scheduled. In Arm 4, all doses for research participants must be taken as scheduled. Failure to comply with these scheduled requirements will result in discontinuation from the study after a final safety evaluation.

Evaluable participants are expected to represent 95% of participants enrolled into the study. No adjustments are made for retention losses since all discontinued or inevaluable participants will be replaced. Each study site will establish participant retention procedures to target lost-to-follow-up rates of <5% in order to minimize additional enrollments to compensate for inevaluable participants.

For the intensive cohort, a subject must have all blood on Days 0, 28, 35 and 49, and vaginal, seminal, and rectal samples on Days 35, and 49 to be evaluable. If the subject is inevaluable for

the intensive cohort, but has met evaluability criteria for the non-intensive cohort AND there is an opening in the non-intensive arm-gender cohort matching the subject, then they may be switched in assignment to the non-intensive cohort. If the intensive subject fails to complete all required samples OR there is not an opening consistent with their gender/arm, then the participant is discontinued after the final safety evaluation. In either case, the subject needs to be replaced in the intensive sampling group.

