## **7.6 Data Analysis**

### **7.6.1 Primary Analyses**

#### **7.6.1.1 Dose Proportionality**

Dose proportionality will be assessed by a confidence interval approach based on the power model, using Day 35 pre-dose concentration ( $C_t$ ) data from all evaluable participants in Arms 1-4. Dose-proportionality will be declared if the 90% confidence interval of the slope completely falls in the critical interval ( $1 + \frac{\ln(0.5)}{\ln(7)} = 0.64, 1 + \frac{\ln(2)}{\ln(7)} = 1.36$ ). Analyte concentrations assessed for dose-proportionality will include TFV and FTC in fluids and their phosphorylated moieties, TFV-DP and FTC-TP, in cells. TFV-DP and FTC-TP will also be assessed in tissue homogenates. Weight-based or creatinine clearance-adjusted intracellular PK parameters may also be used in evaluating dose-proportionality (as well as secondary outcomes). Biological matrices included in the analysis will include: serum, PBMC, CD4+ blood cells, rectosigmoid and vaginal luminal fluid, semen, and rectosigmoid and vaginal tissue specimens (total tissue cells, CD4+ tissue cells, tissue homogenate) (see Table 7-3).

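### The primary dose-proportionality slope uses only the Day 35 trough; averaging in the Day 28 blood trough, already collected and assayed, would be a cheap gain in precision, not the correction of an error

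*Protocol*

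**What the plan says.** Section 7.6.1.1 fixes the primary analysis as a "confidence interval approach based on the power model, using Day 35 pre-dose concentration". The decision rule is: "Dose-proportionality will be declared if the 90% confidence interval of the slope completely falls in the critical interval", with limits 0.64 and 1.36.

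Elsewhere the protocol gives Day 28 much the same standing as Day 35 for blood:

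- Section 7.2.1, primary endpoints in serum, PBMC and CD4+ blood cells: "the following endpoint will be assessed on Day 28 and Day 35 across all 4 dosing arms".
- Section 7.3: "Day 0, Day 28, Day 35, and Day 49 are required for a participant to be considered evaluable".
- Section 2.3.2, purpose of the blood samples: "weekly for 5 weeks (Enrollment and Days 7, 14, 21, 28, and 35) to assess rate of accumulation and dose-proportionality".
- Section 1.2.3: "Dose-proportionality can be assessed at any point of observation following initiation of dosing". It also says that assay variation is "more than twice as large as the very small 4% difference in concentrations that we expect to measure between Day 28 and Day 35".
- Section 7.6.1.2 assumes that both days are at steady state and uses both for intra-participant variability.

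No reason is given for leaving Day 28 out of the slope. Section 7.6.1.1 also covers tissue, luminal fluid and semen, which are sampled only on Days 35 and 49.

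**The concern.** A single trough carries all of a person's occasion-to-occasion and assay noise into the slope. A second trough, at the same time after dosing within each arm and assumed to be at steady state, would halve that part of the variance. The slope's confidence interval decides the first primary objective, so any width removed without new samples is worth having. The matter is precision only. The Day 35 analysis is unbiased for the quantity it targets, and the type I error of the rule is not affected.

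**Working it through.** **Inputs from the protocol.** Four arms of 8 with relative doses 1, 2, 4, 7 (Sections 1.2.2, 7.3). Limits 1 ± ln 2/ln 7 = 0.644 and 1.356. Half-lives 150 h (TFV-DP) and 36 h (FTC-TP) (Table 1-1). CV 25-35% judged realistic, 25-45% explored (Section 7.3). The ICC is not given, because the trial is meant to estimate it; 0.5 to 0.9 is my assumption. Arms 2 and 3 are taken as dosed on days 0 and 3 of each week (Figure 1-1 caption).

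**1. The plan's own figure.** Table 7-1 gives 81.1% power at CV 35% with 8 per arm. Repeating the steps of Section 7.3 (normal draws, 90% interval, a replicate with a non-positive draw counted as a failure) gives 82.1%, against 99.6% and 40.2% at CV 25% and 45% (stated 99.7% and 41.8%). Dropping the non-positive draws instead gives 87.8% and 60.7% at CV 35% and 45%. Because that simulation is so sensitive to this handling, the gains below use lognormal data.

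**2. Does Day 28 change the slope?** With a schedule that repeats weekly, the trough after w weeks is the first-week trough times (1 − q^w)/(1 − q), where q = 2^(−168/half-life). The Day 28/Day 35 ratio is therefore (1 − q^4)/(1 − q^5), the same in every arm.

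- TFV-DP: 0.9552/0.9794 = 0.975. Section 1.2.3 states 93% and 97% of steady state, a ratio of 0.96; this too is common to all arms.
- FTC-TP: 1.000.

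A factor common to all arms moves the intercept and leaves the slope alone.

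**3. Precision.** If each log trough has variance s² and the two correlate at ICC, their mean has variance s²(1+ICC)/2. The SE and interval width are multiplied by sqrt((1+ICC)/2): 0.975 at ICC 0.9, 0.922 at 0.7, 0.866 at 0.5. This is equivalent to 2/(1+ICC) times as many participants: 1.05, 1.18 and 1.33.

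For scale, the sum of squares of log dose over 32 people is 17.10. At CV 35%, s = sqrt(ln(1 + 0.35²)) = 0.340, so the SE is 0.340/sqrt(17.10) = 0.082 and the half-width is 1.697 × 0.082 = 0.14.

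**4. Power, lognormal data, 8 per arm.**

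| Expected means | CV | Day 35 alone | Mean of two days, ICC 0.9 to 0.5 |
|---|---|---|---|
| Proportional (slope 1) | 35% | 99.0% | 99.3% to 99.9% |
| Proportional (slope 1) | 45% | 91% | 93% to 97% |
| Schedule-implied TFV-DP troughs (slope 1.16) | 35% | 74% | 76% to 84% |

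Mean half-widths for the first two rows: 0.138 falls to 0.135-0.120, and 0.175 falls to 0.170-0.151.

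The third row allows for time since last dose, which by the dosing schedule is 7 days in Arm 1, 4 in Arms 2 and 3, and 1 in Arm 4. Superposition with fully linear kinetics then gives TFV-DP troughs in the ratio 1 : 2.39 : 4.79 : 10.0, a slope of 1.16 on either day. For FTC-TP the ratios are 1 : 5 : 10 : 41.5, a slope of 1.81 on either day. That lies outside 1.36, and power is effectively zero with one trough or two.

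**5. Permitted delays.** Section 7.3 allows a 2-day delay in Arms 1-3 during the first three weeks. If the last week-3 dose is delayed, the TFV-DP trough rises as follows:

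| | Day 28 | Day 35 |
|---|---|---|
| Arm 1 | +6.5% | +2.9% |
| Arms 2 and 3 | +3.8% | +1.7% |
| Slope shift if everyone in Arms 1-3 is delayed | −0.028 | −0.013 |

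The average of the two days would then shift by about −0.021, small against a half-width of 0.14.

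**The case against.** **The plan is coherent as written.** A reader might infer from Sections 7.2.1 and 7.3 that a Day 35-only slope contradicts the endpoint definition. It does not. There are two primary objectives, and the second is the Day 28 versus Day 35 comparison, so Day 28 has to be a primary endpoint day and mandatory in any case. The sample-size simulation, the decay analysis and the comparison of men and women all rest on the Day 35 trough, and one pre-specified day is a valid choice. Section 2.3.2 does list Day 28 for dose-proportionality, but jointly with accumulation and alongside Days 7 to 21. All of this stands.

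**The gain may be negligible.** A reader might infer that averaging rescues an underpowered analysis. At the CV of 25-35% that the protocol calls realistic, lognormal power with proportional means is already 99% or more, and the gain is under one point. The ICC could also be high. The protocol's only hint is assay variation of more than twice 4%. With a total CV of 35% and a within-person CV of 10%, ICC = 1 − ln(1.01)/ln(1.1225) = 0.91, and the interval narrows by only about 2%. This stands too.

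**The two days are not interchangeable.** Section 1.2.3 puts them at 93% and 97% of steady state, and permitted delays, which are never allowed in Arm 4, disturb Day 28 more. It would therefore be too strong to say that adding Day 28 can never move the slope; that holds only with dosing on schedule. The effect is small, and a Day 35 sensitivity analysis would reveal it.

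**Different bases.** Blood slopes would rest on two days and tissue slopes on one. This is a real but modest cost. Every primary endpoint in Section 7.2.1 is a blood matrix and has both days.

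None of these points gives a reason not to use a sample that is already in hand.

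**Conclusion.** This is a cheap improvement, not an error. For the blood matrices, using both troughs leaves the expected slope unchanged when dosing is on schedule and narrows its confidence interval by about 13% at ICC 0.5 and 2.5% at ICC 0.9. The ICC range is an assumption. The power gain is under one point at CV 35% with proportional means, about 1 to 6 points at CV 45%, and about 2 to 10 points for TFV-DP at CV 35% if the schedule-implied trough means apply. These figures assume lognormal data, equal variance on the two days, the half-lives of Table 1-1 and linear kinetics.

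The low starting power in the last case comes from unequal time since last dose, which pushes the expected slope to 1.16. Averaging makes that slope more precise but does not move it towards 1. For FTC-TP, with an expected slope of about 1.81, a narrower interval only makes failure to declare proportionality more certain. That is a separate question, and this change should not be presented as an answer to it.

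**What to change.** In Section 7.6.1.1, for serum, PBMC and CD4+ blood cells, define the response in the power model as each participant's mean of the log Day 28 and log Day 35 pre-dose concentrations. A random-intercept model with a day effect would serve equally well. Keep Day 35 alone as a pre-specified sensitivity analysis for blood and as the only analysis for tissue, luminal fluid and semen. State that blood and tissue slopes therefore rest on different bases.

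If the single-day analysis is retained, one sentence saying why Day 28 is not used would settle how Section 7.6.1.1 relates to Section 2.3.2.

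The cost is a sentence or two in the protocol and the matching text in the analysis plan. No new samples or assays are needed, since evaluable participants must have both days and both are assayed for Section 7.6.1.2.

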### 1.1.7 Importance of Dose-proportionality

In order for drug concentration to be used as an adherence measure, the dose-proportionality (i.e., drug concentration at specified times changes proportionally with change in the frequency and amount of drug taken) must be stable at concentrations throughout the adherence range of interest: from concentrations associated with 100% adherence down to concentrations associated with lower levels of adherence. While dose-proportionality is closely related to first order PK,

there are other conditions that will cause disproportionate kinetics, even for a first order drug. Very few drugs exhibit mixed or zero order PK in the clinically relevant concentration range (e.g., aspirin, phenytoin, and fluoxetine). For these drugs, a proportional increase in dose results in a disproportionately large increase in concentration. For other drugs, a proportional increase in dose may result in a disproportionately small increase in concentration. This can be seen in drugs with saturable absorption, and with drugs that are anabolized to phosphorylated forms within cells, such as TFV, FTC, and zidovudine (AZT). For example, because phosphorylation of AZT-monophosphate within cells is the rate-limiting step in AZT-triphosphate anabolism, increasing the AZT dose can result in disproportionately small or no increase in AZT-triphosphate. For either cause of disproportionate PK, the assumption of proportionate change in adherence (as with expected and observed drug concentrations) becomes more complex.

While the dose-proportionality for both TDF and FTC are well-established (Barditch-Crovo et al., 2001; Gish et al., 2002), this proportionality has not been determined for the phosphorylated moieties of these drugs and must be established for one to use TFV-DP or FTC-TP as measures of adherence to a Truvada® (TDF/FTC) regimen.

Other proportionality factors are dose frequency and the accumulation of drug concentration with time – characteristics that are unique to each drug and dosing regimen. Drugs that are dosed at intervals more frequent than their half-life accumulate over time and achieve concentrations that are higher at steady-state than following a single dose. This accumulation – the so-called “accumulation index” or  $R_{ac}$  – varies with the ratio of the drug half-life to dose frequency as follows:

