### **1.2.2 Dosing Regimen Rationale**

We propose to study four different dosing regimens of Truvada® (tablets include 300 mg TDF and 200 mg FTC): one tablet daily, two tablets twice weekly, one tablet twice weekly, and one tablet weekly. To provide adequate data on dose-proportionality, these regimens are selected to cover the range of concentrations achieved between daily and weekly dosing, representing a 7-fold range of anticipated drug concentrations. These regimens will achieve drug concentrations anticipated in current PrEP studies that employ daily dosing, as well as drug concentrations likely to be achieved with proposed intermittent PrEP regimens with dosing as infrequent as weekly or twice weekly dosing. In addition to studying three different dosing frequencies (daily, twice weekly, and weekly), we will study two different doses given twice weekly: a twice-weekly regular dose (one Truvada® tablet), and a twice-weekly double-dose (two Truvada® tablets). This will provide data on dose-proportionality for regimens between the weekly and daily dosing. Using the weekly one Truvada® tablet as reference, these four dosing regimens represent anticipated drug exposures of 1x (weekly), 2x (twice weekly), 4x (double-dose twice weekly), and 7x (daily). These proportions will provide sufficiently rich data to assess dose-proportionality. If dose-proportionality is determined not to hold between weekly and daily dosing, the middle dose regimens provide intermediate points to increase the accuracy with which we can determine the point of deviation from dose-proportionality. Further, they will provide rich drug concentration data to understand these intermediate dosing regimens, which may prove useful in future PrEP efficacy studies should the concentrations of drug prove insufficiently low with weekly dosing.

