Typical sample sizes for phase I PK studies generally range between 6 and 12 subjects per arm. A number of different approaches have been used to assess dose proportionality in the literature (Gough et al., 1995; Hummel et al., 2009; Smith et al., 2000). We consider the sample size using the following two approaches:

1) fitting a simple linear regression model between the PK parameter (y) and dose

$y = \alpha + \beta \text{dose}$ , where the hypothesis that  $\alpha = 0$  is tested and the lack of fit of the model is generally tested by adding a quadratic term; and

2) using the power model approach to fit  $\log(y) = \alpha + \beta \log(\text{dose})$ , where 90% CI around  $\beta$  is

compared to the limits  $(1 + \frac{\ln(\theta_L)}{\ln(r)}, 1 + \frac{\ln(\theta_U)}{\ln(r)})$ , where  $(\theta_L, \theta_U)$  are the pre-defined limits and  $r$

is the ratio of the highest to the lowest dose. The power model and the CI approach has become more preferred choice in recent years (Gough et al., 1995; Smith et al., 2000), however, Hummel et al. (Hummel et al., 2009) suggested that the choice of bioequivalence default values of  $\theta_L = 0.8$  and  $\theta_U = 1.25$  seems to be impractically strict when applied over a dose range that is more than doubling apart and proposed a more lenient criterion  $\theta_L = 0.5$  and  $\theta_U = 2$ .

The empirical power of both approaches are computed using a simulation study with the following steps:

1. Generate random samples of size n from a normal distribution

$N(\mu = 14 \times \text{dose}, sd = CV \times \mu)$ , where 14 is the weekly dosing Day 35  $C_r$  from Figure 1-1, and dose = 1, 2, 4 and 7 for Arm 1 to 4 respectively.

2. Fit linear regression model  $y = \beta_0 + \beta_1 \times \text{dose} + \beta_2 \times \text{dose}^2$  (Smith et al., 2000) and test for nonsignificant intercept and quadratic terms (Zhou et al., 2006).

3. Fit linear model  $\log(y) = \alpha + \beta \log(\text{dose})$  and compare 90% CI of  $\beta$  with the pre-specified critical interval  $(1 + \frac{\ln(0.5)}{\ln(7)} = 0.64, 1 + \frac{\ln(2)}{\ln(7)} = 1.36)$

4. Repeat steps 1-3 for 1000 times. The empirical power is calculated as the proportion of the replications in which nonsignificant intercept and quadratic term holds for approach 1 or the CI falls entirely within the critical interval for approach 2.

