**Table 7-3. Biological matrices for analyses**

	Blood Samples			Vaginal, Rectosigmoid, and Semen Samples			
	Serum	PBMC	CD4+ blood cells	Total tissue cells	CD4+ tissue cells	Luminal fluid & semen	Homogenate
TFV-DP		X	X	X	X		X
FTC-TP		X	X	X	X		X
TFV	X					X	X
FTC	X					X	X

Descriptive statistics, such as means, medians, variance, and interquartile ranges, will be used to summarize Day 35 pre-dose concentration ( $C_t$ ) by gender and by dose arm. Simple comparison of median concentration level between dose arms will be done with standard non-parametric methods. Gender- or dosing-specific CVs of Day 35 pre-dose concentration ( $C_t$ ) will be estimated. These CV estimates would be informative to the future studies even if dose proportionality does not hold.

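### The dose-proportionality verdict rests on one slope that hardly responds to Arm 3, and no fit check or Arm 3/Arm 2 ratio is planned to qualify it if two tablets give no more drug than one

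*Protocol*

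**What the plan says.** Section 7.6.1.1 fits the power model "using Day 35 pre-dose concentration" data from Arms 1 to 4 and states the rule: "Dose-proportionality will be declared if the 90% confidence interval of the slope completely falls in the critical interval". The limits come from Section 7.3, which takes 0.5 and 2 over a 7-fold dose range from a methods paper that, in the protocol's words, "proposed a more lenient criterion". The dose scores are also in Section 7.3: "dose = 1, 2, 4 and 7 for Arm 1 to 4 respectively".

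Section 1.1.7 makes proportionality a matter of both how often and how much drug is taken. Its warning example is a related drug: "increasing the AZT dose can result in disproportionately small or no increase in AZT-triphosphate". Section 1.2.2 says what the inner arms are for, should proportionality fail over the weekly-to-daily range: "the middle dose regimens provide intermediate points to increase the accuracy with which we can determine the point of deviation from dose-proportionality".

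Two other analyses bear on the point. Section 7.3 notes that, for the linear-model approach, "the lack of fit of the model is generally tested by adding a quadratic term"; Section 7.6 does not take this up for the power model. The text after Table 7-3 adds: "Simple comparison of median concentration level between dose arms will be done with standard non-parametric methods".

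**The concern.** Arms 1, 2 and 4 give one tablet per administration and differ only in frequency. Arm 3 alone changes the amount taken at one time. If absorption or phosphorylation saturates within an administration, Arm 3 is where it would show. A single slope over four arms gives an inner point little weight, so a clear failure in Arm 3 could pass unnoticed by the rule.

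Three uses depend on the verdict. A declaration leads to dose-adjusted concentrations in the intra-participant variability analysis (Section 7.6.1.2) and to dose-adjusted pooling of all arms for men against women (Section 7.6.2.2). It is also the premise for a model meant to cover any combination of dose and interval (Section 1.1.2). With true exposures 1:2:2:7, the dose-adjusted levels would be 1/1, 2/2, 2/4 and 7/7, so Arm 3 would sit at half the level of the others. Because Section 1.2.2 turns to the middle arms only after the rule has failed, a false declaration would also close off that search.

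**Working it through.** **Inputs.** Dose scores 1, 2, 4, 7, the limits and the data generator come from Section 7.3. So do 8 per arm and CVs of 25%, 35% and 45%; the protocol calls 25-35% realistic.

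**1. Reproducing Table 7-1.** Limits: 1 ± ln 2/ln 7 = 0.644 and 1.356. The protocol's steps were simulated: normal data with mean 14 × dose and SD = CV × mean, log-log regression, 90% CI within the limits. Some draws are not positive and have no logarithm. Counting those trials as not declared reproduces all 12 power-model cells within 2 percentage points. At 8 per arm it gives 99.6/81.9/40.0%, against 99.7/81.1/41.8% in the table.

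**2. Weight of each arm.** With x = ln(dose) and mean x = 1.006, the deviations are −1.006, −0.313, +0.380 and +0.940. Their squares sum to 2.138.

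| | Arm 1 | Arm 2 | Arm 3 | Arm 4 |
|---|---|---|---|---|
| Slope weight (deviation / 2.138) | −0.471 | −0.146 | +0.178 | +0.439 |
| Share of sum of squares | 47.4% | 4.6% | 6.8% | 41.3% |

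Arms 1 and 4 together supply 47.4 + 41.3 = 88.7%.

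**3. Two tablets equal to one.** Arm 3 halves, so the slope moves by −0.693 × 0.178 = −0.123, to 0.877. At CV 35% with lognormal data, misfit raises the average standard error to 0.108, from 0.340/√(8 × 2.138) = 0.082 under a true fit. A typical lower limit is then 0.877 − 1.697 × 0.108 = 0.69, still above 0.64.

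**4. Chance of declaring proportionality, 8 per arm.**

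| CV | Normal generator: 1:2:4:7 | Normal generator: 1:2:2:7 | Lognormal: 1:2:4:7 | Lognormal: 1:2:2:7 |
|---|---|---|---|---|
| 25% | >99% | 84% | 100% | 89% |
| 35% | 82% | 54% | 99% | 72% |
| 45% | 40% | 24% | 91% | 57% |

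Repeat runs differ by about one point.

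**5. What the data could show.** Arms 2 and 3 share a schedule and the time since last dose. At CV 35% (lognormal) the log ratio has standard error 0.340 × √(2/8) = 0.170, so its 90% CI spans a factor of exp(1.701 × 0.170) = 1.34 either way. A true dose-normalised ratio of 0.5 gives roughly 0.37 to 0.67. With lognormal data this contrast (two-sided 5%, 28 df) detects a complete lack of dose effect in 100/98/88% of trials at CV 25/35/45%. A 2-df lack-of-fit test does so in over 99%, 99% and 90%.

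**6. Which analytes.** Day 35 troughs were computed from the protocol's half-lives, assuming one-compartment accumulation and the Monday/Thursday schedule of Figure 1-1. For TFV-DP (150 h) they are 1:2.4:4.8:10.0, slope 1.16. Halving Arm 3 brings the slope to 1.04, closer to 1, and with the normal generator raises the chance of declaring from 88% to 97% at CV 25% and from 55% to 70% at CV 35%. For FTC-TP (36 h) they are about 1:5:10:42, slope about 1.8, and the rule almost never declares whatever Arm 3 does.

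**The case against.** **The between-arm comparison already covers this.** In part. Read as pairwise, a rank test of Arm 3 against Arm 2 would be significant in 99/88/71% of trials (normal generator, CV 25/35/45%) when doubling works, and in about 5% when it does not. A missing increase could therefore be noticed. But the comparison is not dose-normalised, non-significance is weak evidence, and the result has no bearing on the declaration. Such contrasts are often left to a SAP; the declaration rule, however, is fixed in the protocol without them.

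**The scenario is extreme.** Section 1.2.3 cites proportional plasma tenofovir up to 600 mg, and proportional FTC and FTC-TP in a study that included 400 mg. Saturation that also flattened Arm 4 would move the slope 0.439/0.178 = 2.5 times as much. For adherence, Section 1.1.7 likens missed doses to lower frequency, which Arms 1, 2 and 4 test. This limits the importance. It does not remove the gap, since the same section calls proportionality of the phosphorylated forms undetermined.

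**Stronger readings that the protocol does not support.**
- A reader might infer that the rule cannot see Arm 3 at all. Misfit widens the interval, and declarations do fall (82% to 54% at CV 35%, normal generator).
- A reader might infer that a false declaration is the usual result at any CV. At 45% with the protocol's generator it is 24%.
- A reader might infer that Arm 3 should face the 0.5-2 limits, with a 5% error rate. Those limits apply over the 7-fold range; on a 2-fold step they allow slopes of 1 ± ln 2/ln 2, that is 0 to 2.
- A reader might say that only Arm 3 changes the dose. In the protocol's terms dose runs 1, 2, 4, 7 over all arms; Arm 3 alone changes tablets per administration.

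**Conclusion.** The point holds in a limited form. Over the CV range that the protocol calls realistic, the rule would more often than not declare proportionality although two tablets gave no more drug than one: 84-89% at CV 25% and 54-72% at CV 35%. At CV 45% the range is 24-57%. Nothing in Section 7.6 lets a fit check or an Arm 3/Arm 2 ratio qualify that verdict.

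This rests on exposures of 1:2:4:7, 8 evaluable participants per arm, a common CV, and a failure confined to Arm 3. It applies to TFV-DP, where the computed troughs make the masking stronger rather than weaker. It does not apply to FTC-TP, whose troughs raise a separate problem with the rule. The rule itself can stay; what is missing is an assessment beside it that uses the middle arms for the purpose given in Section 1.2.2.

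**What to change.** In Section 7.6.1.1:

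1. Replace the raw-median comparison by dose-normalised geometric mean ratios between arms, with 90% CIs from the pooled within-arm log variance. Put Arm 3/Arm 2 first, because schedule and time since last dose match. Ratios across different schedules need caution: with linear kinetics the TFV-DP trough ratio Arm 4/Arm 1 is already 10.0/7 = 1.43 after dose normalisation.
2. Add a 2-df lack-of-fit test of the power model, read with the same caution.
3. Report both beside the slope verdict as supportive, and state that any declaration of proportionality is qualified when they show a departure.

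The cost is a little more analysis and reporting, with no new data and no change to the rule's power. Requiring the Arm 3/Arm 2 interval to lie within 0.5-2 before declaring is not advised. Under the protocol's own generator it would cut declarations under true proportionality from 82% to about 72% at CV 35%, and from 40% to 28% at CV 45%. The first figure is below the 81% on which Section 7.3 chose 8 per arm.
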